7. RATIONALE AND BACKGROUND

Alopecia areata (AA) is an autoimmune disease that has an underlying immuno-inflammatory pathogenesis and is characterized by nonscarring hair loss ranging from small patches to complete scalp, face, and/or body hair loss. AA may present as: limited patchy hair loss (patchy alopecia areata), complete loss of hair on the scalp (alopecia totalis [AT]), or complete loss of hair on the scalp and the body (alopecia universalis [AU]). The affected skin usually does not have signs of inflammation.

Both males and females of all ages and races can be affected. AA is the second most common cause of hair loss, affecting approximately 147 million individuals worldwide, with a lifetime risk of all subtypes of approximately 2% (1, 2). Incidence rates of AA range from 20 to 200 per 100,000 person-years [PY(s)], and the global lifetime prevalence worldwide is estimated at 2% (2-8). A meta-analysis including articles published up to 01 September, 2018 estimated the overall pooled incidence proportion of AA in Europe as 4.92% (95% confidence interval [CI] 2.41-8.25%), and the pooled prevalence as 0.58% (95% CI 0.49-0.66%) (9). AA is associated with inflammatory diseases including asthma, allergic rhinitis, atopic dermatitis, and autoimmune diseases such as thyroiditis and vitiligo (10). The natural history and prognosis of AA are unpredictable and can be marked by remission, progression, or persistence (11, 12).

Ritlecitinib was authorized by the European Medicines Agency (EMA), on 15 September 2023, for the treatment of severe alopecia areata in adults and adolescents 12 years of age and older (13). Ritlecitinib is flagged by the Danish authorities as a medication being subject to heightened monitoring (14).

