9.3.3. Risk Factors for Thromboembolic Events

Risk factors for thromboembolic events will be identified during the 12 months prior to and including index date:

- Age >65 years
- History of VTE
- History of arterial thromboembolism (ATE)
- Major surgery within 90 days before the index date
- Combined hormonal contraceptives
- Hormone replacement therapy
- Pregnancy
- Malignancy
- CVD

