9.3.7. Preliminary Operational Definitions of the Main Study Variables

Generally, in the participating data sources, disease is identified by diagnoses recorded at hospitalizations (all three countries) or at hospital-based specialist outpatient clinics (Denmark and Sweden). Diagnoses are currently coded using the World Health Organization (WHO) International Classification of Diseases, Tenth Revision (ICD-10). The Danish version of the ICD-10 may have more detailed codes compared with the WHO ICD-10. ICD-11 will be used if introduced during the study period. Treatment records originate, depending on the database, from outpatient dispensings, from hospital administrations, and are coded using the Anatomical Therapeutic Chemical (ATC) classification or local structured vocabularies (e.g., local treatment codes in Denmark). Ritlecitinib and concomitant medications and vaccinations will be identified using ATC codes or hospital treatment codes as appropriate. Data on laboratory tests, available from Denmark and France, will be identified using Nomenclature, Properties and Units (NPU) codes or local codes as appropriate. Surgeries will be defined using country-specific procedure/surgery codes. Age (date of birth) and sex will be used as reported in the databases.

Table 1 summarizes the initial operational definitions and data availability per data source, of the eligibility criteria, the exposure and the endpoints. The refined, country-specific definitions of all study variables as well as the final list of other variables with their operational definitions will be provided in the Statistical Analysis Plan (SAP).

Table 1. Preliminary Definitions of the Main Study Variables

Measure	Availability and initial operational definition			
	Denmark France		Sweden	
Ritlecitinib initiation	ATC code L04AF08			
Indicators of Adherence to	RMMs			
Lab: lymphocyte count	Potential candidate example codes (subject to refinement): NPU codes NPU02902 B— Neutrophilocytes; NPU02636 B— Lymphocytes; num.c.	Complete blood count including platelets: TNB code 1104	Not available	
Lab: platelet count	NPU03568 B— Thrombocytes	Complete blood count including platelets: TNB code 1104	Not available	
Screening for TB	Not available	In/outpatient lab test (no results)	Not available	
Screening for viral hepatitis B or C	Not available	In/outpatient lab test (no results)	Not available	

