	ICD-10-CM codes to ICD-10 equivalents whenever feasible)			

Table 1. Preliminary Definitions of the Main Study Variables

Risk factors for thromboe	mbolic events, malignancy or C	CVD			
Age 65 years or older	per date of birth				
History of thromboembolic events including VTE or ATE	ICD-10 codes I26, I260A I269 I82.2; I82.3, I82.8, I82.9 O22.3 Denmark only: O882D, O882E	3, O87.0, O87.1	, I81, I82.0,		
Malignancy (any, primary or secondary)	ICD-10 codes chapter C	ICD-10 codes chapter C, treatment codes if relevant	ICD-10 codes chapter C		
Major surgery within 90 days of index date	NOMESCO Classification of Operations on the nervous system: KA; Operations on endocrine organs: KB; Operations on the heart and large intrathoracic vessels: KF; Operations on respiratory organs, chest, mediastinum and diaphragm: KG; Breast surgeries: KH; Operations on digestive organs and spleen: KJ; Operations on the urinary tract, male genitalia and retroperitoneal tissue: KK; Operations on female genitalia: KL; Obstetric operations: KM; Operations on the musculoskeletal system: KN	CCAM codes for major surgery	•		
Combined hormonal contraceptives	ATC codes G03A		Not available (not reimbursed)		
Hormone replacement therapy	AT	C codes G03			
Obesity	ICD-10 codes E65				
Alcohol-related conditions	ICD-10 codes K70, F10				
Tobacco-use related conditions	ICD-1	0 codes J40-J47			
Diabetes	ICD-10 codes F	E10-E14, ATC codes A10	1		

Table 1. Preliminary Definitions of the Main Study Variables

Hypertension	ICD-10 codes I10-I15, treatment proxies			
Hyperlipidaemia	ICD-10 codes E78, treatment p	proxies, laboratory data (l	Denmark only)	
Coronary artery disease	ICD-10 codes I21-I25 Nordic Medico-Statistical Committee (NOMESCO) codes for coronary artery bypass graft (CABG) or percutaneous intervention (PCI): FNF, FNG, FNA, FNB, FNC, FND, FNE	ICD-10 codes I21-I25	ICD-10 codes I21-I25 Nordic Medico- Statistical Committee (NOMESCO) codes for coronary artery bypass graft (CABG) or percutaneous intervention (PCI): FNF, FNG, FNA, FNB, FNC, FND, FNE	
Chronic kidney disease	ICD-10 codes N18, potentially dialysis procedure codes	ICD-10 codes N18	ICD-10 codes N18, potentially dialysis procedure codes	
AA diagnosis	ICD	0-10 code L63		

Source of ICD-10 codes: Denmark and Sweden, inpatient (hospital) or outpatient (specialist visits); France, inpatient hospital encounters. ICD-10 codes with trailing letters are applicable in Denmark only.

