9.4.3. Sweden

Similar to Denmark, the Swedish register system is a large, nationwide source of populationbased data from the entire Swedish population (10.64 million in 2023). Data from the Total Population Register and the Swedish National Health Registers, including the Swedish National Patient Register, Prescribed Drug Register, Total Population Register, Swedish Cause of Death Register, Swedish Medical Birth Register and Swedish Cancer Register will be used. A unique personal identification number is issued to all residents of Sweden upon birth or immigration and is used throughout life. The personal identification number is used to link patient-level data across the various registers. All citizens, independent of socioeconomic status, have unrestricted access to health services including partial or complete reimbursement of purchased medicines due to the tax-supported public health service with universal coverage. The Swedish NPR includes diagnosis information for inpatients at publicly funded hospitals and outpatient specialists' visits, including primary and secondary diagnoses and surgical procedures. The Prescribed Drug Register includes information on all prescribed drugs dispensed at pharmacies in outpatient settings in Sweden since 01 July 2005. The register contains patient level data on dispensed medicines for the entire Swedish population, including information on the dispensed drug as well as the dates of prescription and dispensing (39-43). The coding systems for diagnoses, procedures, and medications are similar in Denmark and Sweden.

All three research centres and associated data sources are listed in the European Network of Centres for Pharmacoepidemiology and Pharmacovigilance (ENCePP) Register.

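### Table 1's preliminary HRT code contains its contraceptive code, and its obesity and tobacco codes do not fit their labels; all three should be corrected before the SAP adopts them

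*Protocol*

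**What the plan says.** Objective 2 describes patients before they start ritlecitinib by their risk factors for thromboembolic events, malignancy and cardiovascular disease (CVD). Section 9.3.3 lists "Combined hormonal contraceptives" and hormone replacement therapy as separate thromboembolic factors. Sections 9.3.4 and 9.3.5 list obesity and tobacco-related conditions as factors for malignancy and again for CVD. Section 9.7, items 8 to 10, reports both the presence and the number of factors.

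The codes are in Table 1 of section 9.3.7:

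- Combined hormonal contraceptives: "ATC codes G03A".
- Hormone replacement therapy: ATC G03, with no subgroup.
- Obesity: "ICD-10 codes E65".
- Tobacco-use related conditions: ICD-10 J40 to J47.

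The same section says that "Table 1 summarizes the initial operational definitions and data availability per data source", and it leaves "The refined, country-specific definitions of all study variables" to the SAP.

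**The concern.** A risk-factor count is meaningful only if each item measures something distinct and each code set matches its label. Here one item's code set is the parent of another's, one label is paired with a neighbouring category, and one proxy includes a disease that the protocol itself ties to the study population: "AA is associated with inflammatory diseases including asthma, allergic rhinitis, atopic dermatitis".

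At stake is the Objective 2 profile in a post-authorization safety study committed to the EMA. Section 9.9 says the risk factors serve to characterise the exposed population. If these codes were carried forward, HRT and tobacco-related conditions would be overstated, obesity would be understated, and the counts would absorb these errors.

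**Working it through.** **HRT and contraceptives.** This follows from the codes alone.

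1. Contraceptive flag: any dispensing with a code beginning G03A. HRT flag: any dispensing with a code beginning G03.
2. Every code beginning G03A also begins G03, so the first set lies inside the second.
3. Hence P(HRT flag) ≥ P(contraceptive flag), whatever the true use of HRT.
4. Section 9.3.3 lists the two separately and section 9.7, item 8, counts them. A woman whose only exposure is a contraceptive scores 2, where the intended score is 1.

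G03A also covers progestogen-only contraceptives in the ATC system, so it is wider than its label of combined products.

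**Obesity.** In ICD-10, E65 is localised adiposity and obesity is E66. The protocol names ICD-10 but does not print these meanings. Neighbouring rows use ranges (E10-E14, I10-I15, J40-J47), so the cell may be a truncated range.

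**Tobacco.** J40-J47 comprises J40, J41, J42, J43, J44, J45, J46 and J47. J45 and J46 are asthma. The proxy enters both the malignancy and the CVD count.

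**Illustration of size.** All shares below are assumptions, taken as proportions of all patients, with overlap treated as independent.

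For scale, the plan's own study size reproduces. With P = 0.5 and e = 0.05, n = 0.25 × 1.96² / 0.05² = 384.16, rounded up to the 385 in Table 2. The 95% half-width at n = 385 is 1.96 × √(h(1−h)/385): 1.4 points at h = 2% and 3.0 points at h = 10%.

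With true HRT share h and G03A share c, measured HRT = h + c − hc:

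| h | c | Measured HRT | Excess (points) |
|---|---|---|---|
| 2% | 5% | 6.9% | 4.9 |
| 2% | 30% | 31.4% | 29.4 |
| 10% | 5% | 14.5% | 4.5 |
| 10% | 30% | 37.0% | 27.0 |

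In each of these cases the excess is larger than the sampling half-width.

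By the same formula, 1-5% with the remaining J40-J47 codes and 2-10% with asthma give a measured tobacco-related share between 0.01 + 0.02 − 0.0002 = 3.0% and 0.05 + 0.10 − 0.005 = 14.5%. If true coded obesity is 3-15% and E65 captures 0-20% of it, measured obesity lies between 0% and 0.15 × 0.20 = 3.0%.

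**The case against.** The strongest reply is status. Table 1 is headed preliminary and refined definitions of all variables are promised in the SAP, where code lists usually belong. That stands against any claim that the reported results will be wrong. It does not make the entries right, because these are affirmative definitions that disagree with their labels. The lymphocyte and serious-infection rows carry their own refinement caveat; the HRT, obesity and tobacco rows do not.

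Section 9.9 concedes that smoking is under-ascertained and inferred from proxies, and the row is labelled tobacco-related conditions rather than smoking. That is fair, but the disclosed error runs downward, whereas including asthma pushes upward. Nothing in section 9.9 touches the overlap of G03 and G03A.

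The table's layout is also damaged in the available text, so a lost continuation of the obesity entry cannot be excluded.

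Three stronger readings are tempting but not supported:

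- A reader might infer that patients with nonmelanoma skin cancer (NMSC) score twice for malignancy, since Table 1 uses all of ICD-10 chapter C. Section 9.3.4 does list NMSC separately, but Table 1 as read gives it no code and the protocol states no rule for overlapping items.
- A reader might infer that the protocol contradicts itself on Sweden. The contraceptive cell marked not available and not reimbursed appears last in its row, while section 9.4.3 says: "The Prescribed Drug Register includes information on all prescribed drugs dispensed at pharmacies in outpatient settings in Sweden since 01 July 2005". The column cannot be relied on, and a limit to reimbursed items matches the French source in section 9.4.2. If the cell is Swedish, double scoring does not arise there, but contraceptive users would still be flagged as HRT users.
- Dropping J47 or adding smoking-cessation drugs to the proxy would be a preference, not the correction of an error.

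**Conclusion.** The point holds in a bounded form. As written, the HRT definition contains the contraceptive definition; that is certain from the codes and needs no assumption. The obesity and asthma mismatches rest on standard ICD-10 meanings, and the obesity one also on the cell being complete. If carried into the SAP, the three codes would bias HRT and tobacco-related prevalence upward and obesity downward. The thromboembolic count would be inflated, and the malignancy and CVD counts would be distorted in both directions.

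The protocol gives no prevalence for any of these factors, so the size of the bias cannot be derived. The illustrative excess of 4.5 to 29.4 points for HRT depends wholly on assumed shares and should not be read as an estimate. No Objective 1 adherence indicator and no study-size figure uses these codes. The matter should be settled before the SAP is final.

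**What to change.** Amend Table 1, or fix the codes in the SAP with a note that they replace Table 1:

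- Make the two hormone variables mutually exclusive. Restrict HRT to estrogen and estrogen-progestogen subgroups such as G03C and G03F, excluding G03A, and restrict the contraceptive variable to combined products within G03A.
- Check whether the obesity cell was truncated, and include E66.
- Remove J45-J46 from the tobacco-related proxy.
- Check which country the contraceptive cell marked not available belongs to, and reconcile it with section 9.4.3.

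The cost is a code-list edit, with no new data and no change in study size. The one small loss is of smokers whose only qualifying code is asthma.

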9.4.2. France

The French nationwide administrative database (Système National des Données de Santé – SNDS; French Administrative Healthcare Database) covers more than 99% of the French population – near 67 million inhabitants – from birth (or immigration) to death (or emigration), even if a subject moves, changes occupation or retires (28, 29). Using a unique pseudonymized identifier, it merges all reimbursed outpatient claims from all French healthcare insurance schemes with hospital-discharge summaries from public and private hospitals, and the national death registry. Thus, all reimbursed medical and paramedical encounters are recorded. SNDS captures general characteristics (e.g., sex, year of birth, affiliation scheme, area of residence); registration for Long Term Disease with the diagnosis code, qualifying for full health insurance coverage; outpatient encounter details (e.g., medical and paramedical visits with practitioner specialty, medical and imaging procedures, laboratory tests, quantity of drugs dispensed, drug strength, medical devices; but no indication, physician prescription directions, drug posology or exam results); inpatient details (e.g., primary and associated hospital discharge diagnoses, procedures and laboratory tests performed, innovative or expensive drugs and medical devices invoiced in addition to the hospitalization, length of the hospital stay). Dates, associated costs, and prescriber and caregiver information are provided for each expenditure. Diagnoses are coded using ICD-10 codes. Drug dispensings are identified and captured through ATC codes, but also at the package level in outpatient settings with the Code Identifiant de Présentation (CIP; Presentation Identification Code), and at the unit of administration level in inpatient settings through the Unité Commune de Dispensation (UCD; Common Dispensing Unit). Procedures are coded according to the Classification Commune des Actes Médicaux (CCAM; Common Classification of Medical Procedures), and laboratory tests follow the Nomenclature des Actes de Biologie Médicale (NABM; Nomenclature of Medical Biology Acts). The SNDS database also includes the French National Death Register (CepiDC) data. Though neither medical indication nor result are recorded, the level of detail of the captured information enables an accurate characterization of patient healthcare journeys (30). SNDS has been used PFIZER CONFIDENTIAL

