9.7. Data Analysis

This is a descriptive study and the data will be analysed and results presented separately by country. Counts and proportions for categorical variables and mean and median with ranges for continuous variables will be calculated to address the study objectives, as below. All proportions will be reported with 95% CIs.

Data sources vary in collection of laboratory test and vaccine information (data on both laboratory tests and their results are available in Denmark; data on performed laboratory tests, but not results, are available in France; laboratory data are not available in Sweden). Data on vaccines are not available in Sweden.

Counts and proportions will be calculated for:

- 1. Patients with evidence of having performed the following laboratory tests and screenings within 3 months before index date:
 - Lymphocyte count
 - Platelet count
 - Screening for TB
 - Screening for viral hepatitis B and C
- 2. Patients with evidence of having performed the following laboratory tests at week 4 (\pm 2 weeks) after index date:
 - Lymphocyte count
 - Platelet count

- 3. Patients with evidence of having received live attenuated vaccines within 4 weeks before index date
- 4. Patients with evidence of having received live attenuated vaccines during treatment with ritlecitinib
- 5. Females in whom pregnancy, as recorded in the available data sources, overlaps with ritlecitinib use
- 6. Patients aged <12 years on the index date
- 7. Patients with a serious infection before index date
- 8. Patients with evidence of having measured risk factors and the number of measured risk factors for thromboembolic events within 12 months before index date
- 9. Patients with evidence of having measured risk factors and the number of risk factors for malignancy within 12 months before index date
- 10. Patients with evidence of having measured risk factors and the number of risk factors for CVD within 6 months before index date

The windows for ascertainment of presence of specific events may be revised to reflect the local data flow.

Detailed methodology for summary and statistical analyses of data collected in this study will be documented in a SAP, which will be dated, filed, and maintained by the sponsor. The SAP may modify the plans outlined in the protocol; any major modifications of primary endpoint definitions or their analyses would be reflected in a protocol amendment.

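### Table 1 marks combined hormonal contraceptives as unavailable in what reads as the Swedish column, for a reason that Section 9.4.3 contradicts; the row also overlaps with the hormone replacement definition

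*Protocol*

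**What the plan says.** Section 9.3.3 lists "Combined hormonal contraceptives" among the risk factors for thromboembolic events, with no exception for any country. Table 1 in Section 9.3.7 defines the variable by "ATC codes G03A" in the first country position and gives "Not available (not reimbursed" in the last. The next row defines hormone replacement therapy by ATC G03, without a country exception.

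On the Swedish source, Section 9.4.3 states: "The Prescribed Drug Register includes information on all prescribed drugs dispensed at pharmacies in outpatient settings in Sweden since 01 July 2005". It adds: "The register contains patient level data on dispensed medicines for the entire Swedish population". On the French source, Section 9.4.2 says that "it merges all reimbursed outpatient claims from all French healthcare insurance schemes".

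The variable feeds item 8 of Section 9.7, which tabulates by country: "Patients with evidence of having measured risk factors and the number of measured risk factors for thromboembolic events within 12 months before index date".

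**The concern.** The reason given for the missing variable does not fit the source it appears to describe. A register of all dispensed prescriptions does not lose a product because it is unreimbursed; a claims database of reimbursed items can. Either the Swedish cell is wrong, or the entry was meant for France and stands in the wrong column.

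At stake is one of the thromboembolic risk factors under Objective 2. If the cell is followed, the Swedish report has no contraceptive line, although the register named for the study can supply one. Item 8 also reports the number of factors per patient, so an error in one factor carries into that number and may carry into the proportion with any factor.

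**Working it through.** The protocol gives no figure for this point, so the check sets the passages side by side and then follows one patient through the definitions.

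**Which column.** The Table 1 header runs Denmark, France, Sweden. The malignancy row has three separate entries, with the French addition of treatment codes in the second position. That makes the last position Swedish, and the contraceptive entry stands there. The position should still be confirmed against the printed table.

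**Does the reason fit Sweden?** Section 9.4.3 attaches no reimbursement condition to the Prescribed Drug Register. The hormone replacement row takes G03 with no Swedish exception, so Table 1 itself treats this ATC group as available there. The Swedish gaps stated in Sections 9.7 and 9.9 are laboratory tests, vaccinations and drugs given or dispensed in hospital; contraceptives are not among them.

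**Does the reason fit France?** Section 9.4.2 limits outpatient data to reimbursed claims. The vaccine row of Table 1 uses lack of reimbursement in the French column, and Section 9.9 repeats this for French vaccines. The contraceptive row shows no such limit for France.

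**What item 8 would count.** Take a patient who uses a combined contraceptive, no hormone replacement therapy, and has no other listed factor. The right answer is one factor, labelled contraceptive. G03A lies within G03 by code prefix.

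| Hormone replacement code set | Country where both rows apply | Sweden as written |
|---|---|---|
| All of G03, as printed | 2 (contraceptive and hormone replacement) | 1 (hormone replacement, wrong label) |
| G03 without G03A | 1 | 0 |

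In the first line the Swedish any-factor count survives under the wrong label, while users are double-counted wherever both rows apply: Denmark, and France if the G03A cell spans both countries. In the second line the double count disappears, but the Swedish patient is missed altogether. Neither line gives the right label and number in every country.

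**Size.** Let c be the proportion of Swedish patients using a combined contraceptive and q the proportion with any other listed factor, taken as independent. In the second line of the table, the shortfall in the any-factor proportion is

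c + q − cq − q = c(1 − q).

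The protocol gives neither input. Purely as assumptions, c from 5% to 30% and q from 10% to 40% give 0.05 × 0.60 = 3 percentage points up to 0.30 × 0.90 = 27 points. In the first line of the table the shortfall is zero. This shows how the result depends on the inputs and on the unsettled definition; it is not an estimate.

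**The case against.** The strongest reply is that the any-factor undercount does not follow from the table as printed, because the broad G03 definition would catch Swedish contraceptive users as hormone replacement users. That stands. A reader might infer that every Swedish user without another factor is recorded as having none; this holds only if the hormone replacement codes are narrowed. The reply does not save the row: the capture is mislabelled, and the same overlap double-counts users elsewhere.

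Second, the country is not certain, since the stated reason suits France better than Sweden. That also stands, and is why the fix begins by asking which country is meant. If the entry is French, Sweden's own definition still has to be stated, and a French gap is missing from Section 9.9.

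Third, a reader might infer that French capture is incomplete and treated as complete. The documents do not support this: Section 9.4.2 openly states the reimbursement limit, and nowhere does the protocol say that a combined contraceptive is unreimbursed in France. The French part is conditional on where the entry belongs.

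Fourth, Section 9.5 rules out comparative analyses, and Section 9.7 presents results by country. An artificial contrast between Sweden and Denmark is therefore not an error in a planned analysis, and showing a French count with and without this factor would not make the countries comparable. The point rests on each country's own result being right.

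Fifth, one could multiply assumed shares of women, of childbearing age and of combined users (0.5 × 0.5 × 0.10 = 2.5% to 0.7 × 0.8 × 0.30 = 16.8%) and call the product the shortfall. It is an assumed prevalence of use from unsourced inputs, not the error in item 8.

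Last, Table 1 is labelled preliminary and the SAP is to refine it. That lowers the stakes, but the table states data availability, and that statement conflicts with the protocol's own account of the source.

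**Conclusion.** The contradiction stands. The Table 1 entry, as placed, cannot be squared with Section 9.4.3 or with the hormone replacement row beneath it. Followed as written, Sweden does not report a listed thromboembolic risk factor under its own label. The overlap of G03 with G03A makes the number of factors per patient wrong in at least one country under either reading of the hormone replacement codes. A shortfall in the Swedish any-factor proportion is possible but not certain.

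The size cannot be derived from the documents. The conclusion rests on the entry standing in the Swedish column; if it is French, the fault is a misplaced limit, an unstated Swedish definition and an omission from Section 9.9. The point concerns recorded risk factors in a descriptive objective. It touches no indicator of adherence to the risk minimisation measures and says nothing about actual thromboembolic risk. It should be corrected, and the correction is small.

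**What to change.** 1. Confirm which country the unavailability entry belongs to.
2. Define the Swedish variable by ATC G03A in the Prescribed Drug Register, as in Denmark.
3. If the reimbursement limit is French, move it to the French cell and state it in Section 9.9.
4. Make the hormone replacement code set exclude G03A, so that no dispensing counts as two factors.

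The cost is an edit to two rows of Table 1 and, if step 3 applies, one sentence in Section 9.9. No new source is needed: the Prescribed Drug Register is already listed for use, and the hormone replacement row already calls for G03. The edit should precede the data applications described in Section 9.6, since a variable marked unavailable may not be requested.
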